- Recruitment, screening, and enrollment of participants
- Protection of participants' rights
- Provide study specific training to the research personnel
- Develop and coordinate randomization scheme and process
- Monitor compliance with protocol and track deviations from the study protocol
- Track, report, and maintain documentation of all serious adverse events and unanticipated problems and disseminating the information to appropriate oversight boards
- Provide periodic updates to affiliated investigators on subject enrollment, general study progress, and relevant scientific advances
- Develop and maintain the MOP
- Retention of specific records (e.g., original consent)

- Development of the data flow and data management procedures, including data entry, error identification, and correction
- AE monitoring and reporting
- Quality control procedures
- Generating and disseminating reports (e.g., enrollment, AEs, participant status, site performance, quality control)

1. STUDY OBJECTIVES

Our long-term objective is to shift the current paradigm away from unimodal, symptom-based care, to an individualized, whole person, behavioral targeted approach for BRLP. In response to current evidence gaps, we are conducting a pilot study to assess the feasibility of a future phase II multi-site randomized clinical trial (RCT). Informed by our previous and ongoing research²⁰ the Integrated **SUPPORTed** Biopsychosocial Self-Management for Back Related Leg Pain trial will assess the comparative effectiveness of a novel supported self-management (SSM) intervention delivered by PTs or DCs versus Medical Care (MC). Importantly, our team has a unique opportunity to leverage recruitment from our ongoing clinical trial (NCCIH UH3AT008769), which excludes a large number of chronic BRLP patients. The R34 aims are:

1.1. Aim One

To conduct a Planning Phase to develop detailed protocols, train personnel, and secure regulatory approvals. We will place special emphasis on working with DCs and PTs to provide competency-based training in the SSM intervention. SSM focuses on whole person care delivery, and integrates psychosocial strategies (e.g. progressive muscle relaxation, relaxed breathing, guided imagery, pacing, relaxation, problem solving, cognitive restructuring, interpersonal communication) with physically oriented ones (e.g. exercises, SMT) *specifically for chronic BRLP*.

1.2. Aim Two

To assess feasibility of the SUPPORT trial through achievement of pre-specified targets for:

- a. Recruiting and enrolling individuals with chronic BRLP by assessing recruitment rates (screens/month; % women and minorities); enrollment rates (participants/month; % women and minorities); and screened participants' views and perspectives (identification of barriers and facilitators for research participation)
- b. Delivering experimental and comparison interventions by assessing acceptability and adherence (% never receiving treatment; % receiving prohibited treatments during intervention phase); % attending required sessions; % participating in home practice and taking medications as directed; % satisfied with treatment); provider intervention fidelity rates (% of required activities delivered) and participant and provider views (barriers and facilitators to engaging in/providing interventions; views regarding affordability, practicality, effectiveness, acceptability, and equity)
- c. Data collection by assessing follow up rates of future clinical trial outcome measures (% of complete assessments at 12 weeks and six months, in addition to % of completed weekly pain surveys)

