6.1. Schedule of Evaluations

(See next page)

Table 5. Pilot Study Data Collection Schedule

Assessment	Initial Screening	Baseline 1	Baseline 2/ Enrollment (Day 0)	Intervention Visits (Month 0-6)	Weekly Follow-Up (Week 1-26)	Monthly Follow-Up (Month 1-6)	Follow-Up (Month 2)	Follow-Up (Month 3)	Follow-Up (Month 6)
Informed Consent	x	x	x						
Demographics	x	x							
Clinical History	x	x							
Physical Exam		x							
Inclusion/Exclusion Criteria	x	x	x						
Quebec Task Force Classification		x							
STarTBack Screening Tool Status		x							
BRLP & LBP frequency & intensity		x	x		x				
Disability, PROMIS-29+2		x	x			x			
Productivity loss, Medication use, Healthcare use			x			x			
Social emotional support, Domain-specific life satisfaction, Perceived stress, Chronic pain acceptance, Chronic pain coping behaviors, Physical activity level, Self-efficacy, Fear-avoidance beliefs, Pain catastrophizing			x					x	x
Treatment expectations			x				x		
Overall satisfaction, Use of key SSM skills, and Global improvement								x	x
Patient-provider connection, healthcare environment							x	x	
Satisfaction with specific components of SBSM								x	
Treatment administered				x					
Adverse events*				x		x			
Qualitative Measures			x					x	
Study close out									x

*Participants can also report adverse events to the PI's or study staff at any point during the trial. **Qualitative data will also be collected from providers regarding their views of barriers and facilitators to care; additionally, as part of supplemental aims, qualitative data will be collected from other stakeholders not taking part in the pilot study to assess their views.

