6.2.4 Follow-up Visits

Intervention Visits (M0-M6)

The following information will be collected at each intervention visit in the pilot study, which will occur as needed throughout the six months, as there is no set schedule of treatments:

- Treatment administered – study providers will record treatment administered at each visit including required, allowed, and prohibited treatments.
- Adverse events (AEs)- participants will be asked about the occurrence of AE/SAEs by their treatment provider at each visit. The AE protocol described in section 7, Safety and Assessments will be initiated and adhered to for all AEs identified.

Weekly Follow-Up (\pm 3 DAYS)

Weekly outcomes will be collected electronically via direct patient self-report for six months; participants who are unable to provide electronic data will be contacted directly by blinded study staff who will ascertain outcomes. Additional information related to data collection and quality assurance is described in section 10.

Clinical Outcome Measures

- BRLP and LBP frequency and intensity

Monthly Follow-up (\pm 14 DAYS)

Monthly follow-up data (Months 1-6) will be collected electronically via direct patient self-report. Participants who are unable to provide electronic data will be contacted directly by blinded study staff who will ascertain outcomes, or they will be mailed a paper copy of the questionnaire to complete and return to the study team. Additional information related to data collection and quality assurance is described in section 10.

The following outcomes will be collected on a monthly basis for 6 months (\pm 14 days):

Clinical Outcome Measures

- Disability, PROMIS-29+2 measures, and productivity loss
- Adverse Events - participants will be asked if they experienced any potential adverse events associated with study interventions (e.g. increased pain, neurological symptoms, nausea)

Behavioral Outcome Measures

- BRLP-related medication and healthcare use

Month 2 Follow-up (\mp 14 DAYS)

Mediating Outcome Measures

- Satisfaction related to the patient-provider connection and healthcare environment (HEAL items).¹³⁵ Treatment expectations for the assigned intervention will also be assessed.

Month 3 Follow-up (\mp 14 DAYS)

Clinical Outcome Measures

- PROMIS/NIH Toolbox measures for social emotional support, domain-specific life satisfaction, and perceived stress.
- Global improvement will be measured using a 9-point scale ranging from completely recovered to vastly worse.¹⁵⁴

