6.2.5. Compensation

There is no cost for participation in the study. Participants and their insurers will not be billed for study screening and treatment visits. Participants in the pilot study will be compensated a total of \$150.00 for time associated with participating in the study, in the form of a UMN ClinCard. Participants are not compensated for attending screening and/or intervention study visits. ClinCards will be administered at an in-person study visit or via mail following enrollment in the study. The following compensation scheduled will be used:

80% of weekly surveys completed	\$40.00
Month 1 follow-up completion	\$10.00
Month 2 follow-up completion	\$10.00
Month 3 follow-up completion	\$40.00
Month 4 follow-up completion	\$10.00

Month 5 follow-up completion	\$10.00
Month 6 follow-up completion	\$30.00

In addition, prescription and over-the-counter medications recommended for participants in the MC group will be paid for by the study. Study staff will load cards with funds for participants to pay for their study medications. ClinCards will be administered at an in-person study visit or via mail following enrollment in the study.

For the supplemental aims qualitative interviews, participants will be compensated \$50.00 per interview.

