9.4. Outcomes

9.4.1. Primary Outcomes

Primary outcomes for the pilot study are feasibility measures for the larger randomized trial including:

- Recruitment feasibility - Number of participants screened per month; percentage of screened participants who are female; percentage of screened participants who are minorities; participant views and perspectives on research participation
- Enrollment feasibility - Number of participants enrolled per month; percentage of enrolled participants who are female; percentage of enrolled participants who are minorities; participant views and perspectives on research participation
- Intervention acceptability and credibility feasibility - Percentage of enrollees not receiving any treatment; percentage of enrollees receiving prohibited treatments during the 12-week intervention phase (contamination); percentage of enrollees satisfied with treatment

- Participant treatment adherence feasibility - Percentage of enrollees attending required sessions; percentage of enrollees in the supported biopsychosocial self-management group reporting participation in home practice; percentage of enrollees in medical care group reporting taking medications as prescribed
- Provider fidelity feasibility - Percentage of provider visits where 100% of required intervention activities were delivered
- Data collection feasibility - Percentage of enrollees completing the month 3 assessment; percentage of enrollees completing the month 6 assessment; percentage of weekly pain severity and frequency assessments completed

Table 6. Feasibility Measures & Targets

Recruitment	≥40 screened/month (50% women, 25% minorities)
Enrollment	≥8 enrolled/month (50% women, 25% minorities)
Intervention acceptability, credibility	≤10% never receive any treatment; ≤10% receive prohibited treatments during 12-week intervention phase (contamination) ≥80% satisfied with treatment
Participant adherence	≥80% participants attend required sessions (SSM=4; MC=2) ≥70% of SSM participants report participation in home practices ≥70% of MC participants report taking medications as prescribed
Provider fidelity	Providers deliver 100% of required intervention activities on ≥70% of visits
Data collection	≥85% of participants complete 12 weeks follow up ≥80% of participants complete 25-week follow up ≥80% of weekly pain severity and frequency surveys completed

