9.5. Data Analyses

Feasibility outcomes (Aims 2a-2c) will be assessed using a combination of descriptive statistics and qualitative analyses (described under Protocol refinement measures). For AIM 2a, we will determine the mean number of participants screened/month and enrolled/month in addition to the percentage of women and minorities screened and enrolled. For AIM 2b, we will report the percentage of enrolled participants compliant with treatment protocols by group (visit attendance, home practice, contamination) and

percentage of treatment visits delivered according to protocol (provider fidelity). For AIM 2c, percentage of outcome assessments completed at 12 weeks and 6 months will be described, in addition to the percentage of weekly pain severity and frequency assessments completed.

Protocol refinement measures will be analyzed and presented descriptively in a similar fashion as described above. Qualitative data (collected via open-ended questions in REDCap surveys, and transcribed interviews), will be analyzed using template style qualitative content analysis informed by the conceptual framework for the study (see Figure 2).^{89,106,137-139} by study team members with qualitative research experience.^{21,89,90,136} Representative quotations will be identified during the coding process, and coded themes will be quantified by categorizing them as present or absent for each case, and presented as frequencies.¹³⁹

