10.3.4. Metrics

For each follow-up survey, we aim to achieve an 85% or higher follow-up rate. We will utilize a combination of web-based survey, telephone and text-based outreach, and mailed surveys to achieve maximal survey response. Survey completion rates will be primarily based upon the completion of pain and functional outcome measures, but we will additionally tabulate follow-up by each instrument to monitor and evaluate survey burden. Data on other key feasibility measures and targets will also be reviewed weekly

by the PIs and monthly by the Study Steering Committee (e.g. recruitment rates, enrollment rates, intervention acceptability, credibility, and adherence, provider fidelity, adverse event reporting).

Loss to Follow-Up: Participants are considered loss to follow-up if any of the criteria below are met:

1. Participant dies
2. Participant formally withdraws from the study
3. Participant misses 3 consecutive monthly and 8 consecutive weekly surveys without responding to reminders by email (at least 3) or phone (at least 3).

Participant's meeting criteria 3 can have their loss to follow up status removed if they contact the study and request continuation of data collection activities.

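### Leg pain is rated after baseline only in the weekly surveys, and their single 80% target has no time window, so every data-collection target can be met with few leg-pain ratings near month 6.

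*Combined protocol and SAP*

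**What the plan says.** Aim 2c in section 1.2 sets out to show that the future trial's outcome measures can be collected. It measures the percentage "of complete assessments at 12 weeks and six months, in addition to % of completed weekly pain surveys".

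In Table 5 (section 6.1) the row "BRLP & LBP frequency & intensity" is marked at the two baseline visits and in the weekly column, headed "Weekly Follow-Up (Week 1-26", and nowhere else. Section 6.2.4 agrees: "Weekly outcomes will be collected electronically via direct patient self-report for six months", with leg and back pain intensity and frequency as the content. The monthly list has disability, PROMIS-29+2 and productivity loss. The Month 3 and Month 6 lists add social support, life satisfaction, stress, global improvement, behavioral and mediating measures. None contains a leg-pain rating.

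Table 6 (section 9.4.1) has three data-collection targets: at least 85% at 12 weeks, at least 80% at 25 weeks (month 6 in the text above the table), and "≥80% of weekly pain severity and frequency surveys completed". Section 9.5 plans the two assessment percentages "in addition to the percentage of weekly pain severity and frequency assessments completed". No denominator, window or split by week is given.

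The payment rule in section 6.2.5 uses the same form: "80% of weekly surveys completed" earns $40. Section 10.3.4 adds an aim of 85% for each follow-up survey and states: "Survey completion rates will be primarily based upon the completion of pain and functional outcome measures".

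**The concern.** The two targets tied to a time point apply to surveys without a leg-pain rating, and the one target that concerns leg-pain ratings is tied to no time point. Aim 2c asks about follow-up at 12 weeks and six months. For leg-pain intensity and frequency, which head the clinical outcome list in section 6.2.2, the plan's criteria do not answer that question.

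The pattern that exposes the gap is weekly-survey fatigue: a participant stops, or largely stops, the short weekly survey but still answers the monthly ones. The loss-to-follow-up rule in section 10.3.4 would not catch this person, because its third criterion requires three consecutive monthly and eight consecutive weekly surveys to be missed together. The pilot could then report all data-collection targets as met, and the planners of the larger trial would have no prespecified figure for how many participants had a leg-pain rating near month 6.

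**Working it through.** **Inputs.** 26 weekly surveys per participant (Table 5); 40 to 50 participants (sections 6.2.2 and 9.1); targets of 85% at 12 weeks, 80% at 25 weeks and 80% of weekly surveys (Table 6). The plan derives no figure here that could be reproduced; the 80% is a chosen threshold. Because no window is stated, I read it as pooled over all survey-weeks.

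**1. Surveys needed.** Due: 40 × 26 = 1040 or 50 × 26 = 1300. Needed: 0.80 × 1040 = 832 or 0.80 × 1300 = 1040. Up to 208 or 260 may be missing, in any weeks.

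**2. Logical bound.** If everyone answers weeks 1-21 and nobody answers weeks 22-26, completion is 21/26 = 80.8% (840/1040 or 1050/1300). The target is met with no rating after week 21. To leave only weeks 24-26 empty, weeks 1-23 need 20.8/23 = 90.4%.

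**3. Plain permanent dropout.** Let retention be S(t) = exp(−λt), with everyone retained answering every week. Setting the mean of S over weeks 1-26 to 0.80 gives λ = 0.0171, so S(12) = 81.4%, S(25) = 65.1% and S(26) = 64.0%. Those who left are also missing from the monthly surveys, so both assessment targets fail (81.4% < 85%; 65.1% < 80%). The plan would not report success.

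**4. Dropout plus sporadic missed weeks.** Assume those retained answer 90% of weeks. Setting 0.90 × mean S(t) = 0.80 gives λ = 0.0089, with retention 89.9% at week 12, 80.1% at week 25 and 79.4% at week 26. Week 26 alone stands at 0.90 × 79.4% = 71.4%. If misses are independent, those retained to week 26 with at least one rating in weeks 24-26 are 79.4% × (1 − 0.1³) = 79.3%. This is essentially no shortfall against 80%.

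**5. Weekly fatigue among people who still answer the monthly surveys.** Let retention be R^(t/26), ending at R at week 26. Let weekly response among those retained fall linearly from 100% at week 1 to e at week 26. Solve for e so that the pooled rate is 80%.

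| R | e | Week 26 = R × e |
|---|---|---|
| 0.80 | 0.784 | 62.8% |
| 0.95 | 0.640 | 60.8% |

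With R = 0.80, retention is 0.80^(12/26) = 90.2% at week 12 and 0.80^(25/26) = 80.7% at week 25. If everyone retained answers the monthly surveys, all three targets are met. The week 26 rating is present for about 24 to 25 of 40, or 30 to 31 of 50. An 80% standard would need 32 or 40.

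**6. The same scenario in a three-week window.** If those who stop the weekly survey stay stopped, the share with any rating in weeks 24-26 equals the week 24 figure. For R = 0.80: 0.80^(24/26) × (1 − 0.2155 × 23/25) = 0.814 × 0.802 = 65%. For R = 0.95: 0.95^(24/26) × (1 − 0.3602 × 23/25) = 0.954 × 0.669 = 64%. If misses are scattered at random, nearly everyone retained would have a rating, as in step 4. The gap therefore depends on lasting withdrawal from the weekly survey.

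**The case against.** The strongest reply has four parts.

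- **Month 6 is not without pain data.** PROMIS-29+2, which includes pain interference, and the Roland Morris questionnaire adapted for BRLP are collected every month. A reader might infer that the targets could be met with no pain information at all at month 6; the schedule does not support that. This stands, and the point is limited to intensity and frequency ratings.
- **Ordinary attrition is already caught.** Steps 3 and 4 bear this out: pure dropout fails the other targets, and scattered misses leave almost no gap in a three-week window. This also stands. It narrows the point to weekly fatigue, for which the protocol gives no direct evidence. The team's earlier acute low back pain pilot reached 94% weekly completion (section 2.2). A pooled 94% under steady dropout would still leave about 89% at week 26.
- **Monitoring would show it.** Section 10.3.4 aims for 85% on each survey and tabulates by instrument, section 10.3.3 has rates reviewed weekly, and section 9.4.2 lists missing variables and reasons for missed assessments. A late collapse would probably be seen. But section 14 ties feasibility to Table 6, and the 85% per survey is not a Table 6 criterion.
- **Payment does not simply switch off after week 21.** That is true only for someone who answered all of weeks 1-21; a person with earlier misses still needs later weeks to reach 21 of 26, and Month 6 carries its own $30. The payment rule does not target the time points, but it is no evidence that late surveys will be missed.

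**Conclusion.** The point holds in a limited form. Table 6 contains no criterion for leg-pain intensity or frequency at week 12 or month 6, and all three data-collection targets can be met while those ratings are sparse near month 6. The bound is zero ratings after week 21 at 80.8% pooled completion; this is a limit, not a forecast. Under gradual weekly fatigue with a pooled rate of exactly 80%, week 26 stands at about 61-63%, and at 64-65% for any rating in weeks 24-26 if those who stop do not resume.

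These figures assume a pooled denominator, retention of 80-95% at week 26, a linear fall in weekly response, and monthly surveys answered by everyone retained. At completion near the earlier pilot's 94% the gap would be small. The weakness matters when results are close to the threshold, which is where a prespecified criterion has to discriminate.

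A reader might go on to infer that the phase II attrition assumption would be wrong. The protocol states no phase II primary outcome, time point or attrition figure, so that does not follow. The consequence depends on leg pain at these times being an endpoint there.

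**What to change.** In section 9.4.1, Table 6 and section 9.5, add the percentage of enrolled participants with at least one weekly BRLP rating in a window around week 12 (for example weeks 11-13) and around month 6 (for example weeks 24-26). Hold these to the existing 85% and 80% targets: 34 of 40 or 43 of 50 at week 12, and 32 of 40 or 40 of 50 at month 6. Tabulate weekly completion by week, and keep the pooled percentage as a description with its denominator stated.

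This uses data already scheduled and adds no visits or questions. The cost is a little more tabulation and a completion figure that may look less favourable.

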1.3. Supplemental Aims

In addition to the primary aims, NCCIH approved the following supplemental aims as part of the parent R34 pilot study. These aims address the original objective of assessing the feasibility of a future phase II RCT, with additional emphasis on engaging individuals often underrepresented in CIH back pain research.

1. To develop procedures and processes that transparently define how researchers and community members will work together on the proposed research.

APPROACH: Based on the literature, preliminary work and collaboration with a Community Advisory Team, we will develop clearly articulated manuals of operations, including a collaborative team charter that describes how researchers, the Community Advisory Team, and community members will work together on the parent trial and beyond.

2. To explore and describe the barriers and facilitators underrepresented populations encounter in relation to participating in CIH back pain research.

APPROACH: We will collect qualitative data from an additional sample of community members (n=20-30) from traditionally underrepresented groups and use deductive analyses using established models and frameworks.

3. To develop community-informed study procedures and materials and assess community members' and participants' views of them.

APPROACH: We will use an iterative design, development, implementation, and evaluation process successfully used by our team, to create recruitment, screening, enrollment, intervention, monitoring, and dissemination processes and materials that are culturally sensitive and meet diverse participant needs in relation to engaging in CIH pain research.

